## 13.2 REPORTING ADVERSE EVENTS

**Adverse Events** should be recorded on the appropriate CRF.

All **SAEs** should be reported to the sponsor within 24 hours of the Clinical Investigator becoming aware of the event fulfilling the criteria. The SAE form should be completed and emailed to the Clinical Trials Manager and Joint Research Compliance Office. The minimum criteria required in reporting a SAE are the participant identifiers (Trial ID/Date of Birth), reporting source (name of Investigator), and why the adverse event is identifiable as serious.

**Other important adverse events** that should be reported to the sponsor within 24 hours of the Clinical Investigator becoming aware of the event, include

- allergic bronchospasm requiring intensive emergency treatment
- a seizure
- any adverse event that results in **discontinuation of the immunisation schedule**
- any adverse event that requires intervention to prevent a threat to life or death

### SAE REPORTING AND IMPORTANT AE NOTIFICATION

Within 24 hours of becoming aware of an SAE or important AE, please complete the SAE form, and email the coordinating centre (Clinical Trials Manager) to notify on:

### SAE REPORTING AND IMPORTANT AE NOTIFICATION

Investigators should notify the Coordinating Centre of all SAEs within 24 hours of the investigator becoming aware of the event, from the time of registration until the end of trial. SARs and SUSARs must be notified to the Coordinating Centre until trial closure.

Upon receipt of a SAE form at the Coordinating Centre, the PI (or a medically-qualified delegate) will review all SAE reports received. The causality assessment given by the local investigator at the hospital cannot be overruled; in the case of disagreement, both opinions will be provided in any subsequent reports.

The PI will assess whether the event qualifies in seriousness and relationship as a **Suspected Unexpected Serious Adverse Reaction (SUSAR)**. Fatal and life-threatening SUSARs must be reported to the MHRA within 7 days of day 0 which is defined as the day the sponsor became aware of the event. Relevant follow-up information should be sought and a further report completed as soon as possible and submitted within 8 additional days. SUSARs which do not result in death or a threat to life should be reported within 15 days of day 0. Ultimate responsibility for classification resides with the study Sponsor.

The team at the Coordinating Centre is primarily responsible for the reporting of SUSARs and other SARs to the sponsors and regulatory authorities (MHRA and competent authorities of other European member states and any other countries in which the trial is taking place) and the research ethics committees, as appropriate. The study team at the Imperial CRF will act as back-up to the Coordinating Centre in this respect.

### 13.2.1 PREGNANCY

Pregnancy is not an adverse event. However, it is a reportable event in a Phase I trial, and should be reported to the PI within 24 hours of the Clinical Investigator becoming aware of the pregnancy by email, fax or phone.

All pregnancies will be followed up to collect information about the outcome which will be recorded in the clinical study report.

### 13.2.2 REPORTING SERIOUS BREACHES

In the event of a serious breach, the site will inform the Coordinating Centre as soon as they are aware of a possible serious breach of compliance, so that the Coordinating Centre can report this breach if necessary within 7 days as per the UK regulatory requirements. The study team at the Imperial CRF will provide back-up in this respect. For the purposes of this regulation, a 'serious breach' is one that is likely to affect to a significant degree:

- The safety or physical or mental integrity of the subjects in the trial, or
- The scientific value of the trial

## 13.3 INVESTIGATOR RESPONSIBILITIES AND ASSESSMENTS

All non-serious AEs and ARs, whether expected or not, should be recorded in the source documents and CRF. SAEs and SARs should be notified to the Coordinating Centre and the JRCO within 24 hours of the investigator becoming aware of the event.

### 13.3.1 SERIOUSNESS

When an AE or AR occurs, the investigator must first assess whether or not the event is serious using the definition given **Table 4**. If the event is serious then an SAE Form must be completed and the Coordinating Centre notified within 24 hours.

**13.3.2 SEVERITY OR GRADING OF ADVERSE EVENTS**

The severity of all AEs and/or ARs (serious and non-serious) in this trial should be graded using the toxicity gradings in **Appendix 1**.

**13.3.3 CAUSALITY**

The investigator must assess the causality of all non-solicited adverse events or reactions in relation to each of the trial IMPs using the definitions in **Table 5**. There are five categories: unrelated, unlikely, possible, probable, and definitely related. If the causality assessment is unrelated or unlikely to be related, the event is classified as an AE. If the causality is assessed as possible, probable or definitely related, then the event is classified as an SAR.

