**12.6 CRITERIA FOR STOPPING TREATMENT GROUPS OR WHOLE TRIAL**

All trial immunisations will be put on hold in the event of a SAR or two severe ARs, and in the event of every subsequent SAR or severe AR.

In the event of a SAR, the PI should notify the sponsor within 24 hours of becoming aware, and the PI will arrange for any necessary expert reviews to take place.

Further immunisations will be put on hold until the review is completed.

A component of any expert review will be to consider whether or not further immunisations should be discontinued in the individual, and/or the trial.

If immunisations are put on hold, the TMG will determine whether or not to call an unscheduled meeting of the Independent Data Monitoring Committee (IDMC) to review the safety data, and whether or not to hold further immunisations until this has taken place. If an unscheduled IDMC is warranted, the Sponsor will be informed and the IDMC asked to make a recommendation to the Principal Investigator and the Sponsor about continuing further immunisations.

At any time if the study is put on hold (for example following the occurrence of a SAR) the Regulatory authority has to be informed of the temporary halt and a substantial amendment with relevant data has to be submitted to the MHRA for approval in case a decision to resume dosing is taken. The Sponsor reserves the right to stop the whole trial at any time.

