**TABLE 4 TYPES OF ADVERSE EVENTS AND DEFINITIONS CONTINUED**

Type of Event	Definition
Unexpected Adverse Reaction (UAR)	An adverse reaction, the nature or severity of which is not consistent with the information about the medicinal product in question set out in the Summary of Product Characteristics (SPC) or Investigator Brochure (IB) for that product.
Serious Adverse Event (SAE) or Serious Adverse Reaction (SAR) or Suspected Unexpected Serious Adverse Reaction (SUSAR)	
Respectively any adverse event, adverse reaction or unexpected adverse reaction that:
 
 
• Results in death
 
• Is life-threatening*
 
• Requires hospitalisation or prolongation of existing hospitalisation**
 
• Results in persistent or significant disability or incapacity
 
• Consists of a congenital anomaly or birth defect
 
• Is another important medical condition***
 
 
Notes:  'A threat to life' refers to an event or reaction in which the patient was at risk of death at the time of the event; it does not refer to an event or reaction which hypothetically might have caused death had it been more severe.
 
If an AE is serious and unexpected and considered possibly, probably or definitely related to study product according to the classification below then it meets the criteria for a SUSAR and should be reported accordingly.

\*The term life-threatening in the definition of a serious event refers to an event in which the patient is at risk of death at the time of the event; it does not refer to an event that hypothetically might cause death if it were more severe, for example, a silent myocardial infarction.

\*\*Hospitalisation is defined as an inpatient admission, regardless of length of stay, even if the hospitalisation is a precautionary measure for continued observation. Hospitalisations for a pre-existing condition, that has not worsened or for an elective procedure do not constitute an SAE.

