**TABLE 5 - ASSIGNING TYPE OF AE THROUGH CAUSALITY**

Relationship to study product classified as:

[figure not shown]
Relationship	Description	AE Type
Unrelated	There is no evidence of any causal relationship	Unrelated AE
Unlikely	There is little evidence to suggest that there is a causal relationship (for example, the event did not occur within a reasonable time after administration of the trial medication). There is another reasonable explanation for the event (for example, the patient's clinical condition, other concomitant treatment).	Unrelated AE
Possible	There is some evidence to suggest a causal relationship (for example, because the event occurs within a reasonable time after administration of the trial medication). However, the influence of other factors may have contributed to the event (for example, the patient's clinical condition, other concomitant treatments).	AR
Probable	There is evidence to suggest a causal relationship and the influence of other factors is unlikely.	AR
Definitely	There is clear evidence to suggest a causal relationship and other possible contributing factors can be ruled out.	AR

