#### **14.5.4 SAFETY OUTCOMES**

The AEs will be coded using MedDRA. If a participant reports the same event more than once then the worst severity and worst relationship to trial vaccine will be taken. Discrepancies between diary card and CRF reports will be queried by the monitor if unclear. It is assumed that the grade assigned by the clinician is more accurate, and this will be the grade reported in the tables. If the diary card grade is worse, this will be foot noted.

Safety outcomes will be reported overall with proportion and 95% confidence interval, and by group and time-point, and by relationship to study product, and method.

For the primary analysis of safety and tolerability endpoints (as defined in section 14.2), results will be expressed as a proportion with confidence interval.

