12.2.2 Safety and Tolerability

Safety data analysis will be based on the safety population and procedure described in here is applicable for both part 1 and part 2.

The following table illustrates the schedule used in capturing and monitoring adverse events.

Visit		1	2	3	4	5	6	7	8	9	10	11
Study Month		M0			M3			M6				M12
Study Week		W0	W1	W4	W12	W13	W16	W24	W25	W26	W28	W48
Study Day		D0	D7	D28	D84	D91	D112	D168	D175	D182	D196	D336
Visit Windows (Days)	-90		±1	±2	(±7/+14)	±1	±2	(±7/+14)	±1	±2	±2	±14
Solicited Adverse Events		X ⁶	X		X ⁶	X		X ⁶	X			
Review Solicited AE on diary card			X			X			X			
Unsolicited Adverse events		X ⁶	X	X	X ⁶	X	X	X ⁶	X	X	X	
Serious adverse events		X	X	X	X	X	X	X	X	X	X	X

Information on three different types of adverse events/reactions were collected at various timepoints, particularly pre- and post- vaccination on the day, throughout the study namely the serious, solicited, unsolicited adverse events. Adverse events/reactions are categorised both in terms of the severity (graded 1-4) and relatedness to the IMP (unrelated, unlikely, possible, probable, and definitely related).

As part of the safety and tolerability aspect of the primary endpoint reporting, the following will be reported,

- The frequency and percentage of participants with vaccine-related serious adverse events (SAEs) throughout the study period
- The frequencies and percentages of participants with severe or greater (Grades 3-4) adverse reactions at each time point during the study will be reported.

In addition to that, the frequencies and percentages of all adverse events/reactions separately for solicited, unsolicited and in combination will be reported and grouped by time point (separately for each time points and for all time points combined), severity

(graded 1-4) and relatedness (unrelated, unlikely, possible, probable, and definitely related). Whenever possible results will be split between arm 1 and arm 2 in part 1.

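### Three safety rules need correction: the SAR label in Protocol 13.3.3, the repeat-event rule in Protocol 14.5.4, and the reporting specified in SAP 12.2.2

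*Protocol*

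**What the plan says.** **Label.** Protocol 13.3.3 opens with its scope: "The investigator must assess the causality of all non-solicited adverse events or reactions in relation to each of the trial IMPs". It then states: "If the causality is assessed as possible, probable or definitely related, then the event is classified as an SAR". No seriousness condition is attached. Table 5, to which the same section refers, types the possible, probable and definite categories as AR. Its probable category, for example, reads "There is evidence to suggest a causal relationship and the influence of other factors is unlikely" and is an AR. Table 4 defines SAE, SAR and SUSAR together as "Respectively any adverse event, adverse reaction or unexpected adverse reaction that" meets one of the listed seriousness criteria. Section 13.3.1 has seriousness judged first, by Table 4. Section 12.6 then acts on the label: "All trial immunisations will be put on hold in the event of a SAR or two severe ARs".

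**Repeats.** Protocol 14.5.4 covers a participant who reports the same event more than once: "then the worst severity and worst relationship to trial vaccine will be taken". It does not say that the two must come from the same occurrence.

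**Reporting.** The same section says: "Safety outcomes will be reported overall with proportion and 95% confidence interval, and by group and time-point". It asks again for a confidence interval on the primary safety endpoints. SAP 12.2.2 gives frequencies and percentages, and reports participants with Grade 3-4 reactions at each time point. Its only stated split by treatment is: "Whenever possible results will be split between arm 1 and arm 2 in part 1".

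**The concern.** The two primary safety endpoints are the proportion of participants with a Grade 3-4 adverse reaction during the study and the proportion with a vaccine-related SAE. Each is simple to count if seriousness, grade and relatedness are kept apart and attached to the same occurrence. The documents loosen this in three places.

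- Read literally, 13.3.3 turns a mild, possibly related unsolicited event into an SAR. Under 12.6 one SAR stops dosing across the trial. After a hold the regulator must be informed, and resuming needs a substantial amendment.
- The rule in 14.5.4 can join the grade of one occurrence to the causality of another, which feeds the Grade 3-4 endpoint directly.
- The SAP does not carry over the by-group results and intervals that the protocol promises. Groups A and E are the controls for the Ad4 vector, and Protocol 7.8 says there are no clinical data for Ad4-EnvCN54. A split by arm puts one control group inside each arm.

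**Working it through.** **Plan's own figure.** The only precision statement is Protocol Table 7 (n = 6, Clopper-Pearson 95%). The rows for 1/6 to 6/6 reproduce; 1/6, for example, gives 0.4% to 64.1%. The 0/6 row does not. The two-sided exact upper limit is 1 − 0.025^(1/6) = 45.9%, against the printed 39%. The printed value matches a one-sided 95% limit, 1 − 0.05^(1/6) = 39.3%, or a Wilson limit of 39.0%. The point does not rest on this row, but safety tables in groups of 6 may well contain zeros.

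**1. SAR label.** Take one non-serious, possibly related, unsolicited event through each section:
- 13.3.1 and Table 4: not serious, so not an SAR.
- Table 5: AR.
- 13.3.3: SAR.
- 12.6: a hold if it is an SAR. If it is an AR, the hold rule depends on whether it is severe and how many there have been.

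The same event therefore has two labels, with different consequences. Solicited events starting within 7 days of a vaccination are outside 13.3.3; Table 4 makes them ARs automatically.

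**2. Repeat events.** Suppose a participant has a Grade 1 headache on day 2 (related by rule) and a Grade 3 headache weeks later judged unrelated.
- By occurrence: no record is both Grade 3-4 and related, so the participant is not counted.
- Under 14.5.4: worst grade 3 and worst relationship possible, so the participant counts as having a Grade 3 adverse reaction.

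To find the direction of the error, enumerate all ordered pairs of records, each with 4 grades and 5 causality categories: 20 × 20 = 400 patterns. A false positive needs one record that is Grade 3-4 and unrelated or unlikely (2 × 2 = 4 types) and one that is Grade 1-2 and related (2 × 3 = 6 types). That gives 4 × 6 × 2 orders = 48 patterns. There are no false negatives. This counts patterns and is not a probability. In a group of 6, one false event moves the estimate from 0/6 = 0% to 1/6 = 17%.

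**3. Grouping and intervals.** Protocol 11.1 gives 36 Part 1 participants on Ad4 and 12 on oral placebo. By Table 1 that is 18 and 6 in each arm. With event rate p1 in Ad4-primed and p0 in placebo-primed participants, the arm shows (18·p1 + 6·p0)/24.
- Assumed p1 = 20%: the arm shows 15%, 17.5% or 20% for p0 = 0%, 10% or 20%. Dilution is at most a quarter in relative terms, and nil when the rates are equal.
- Three events, all in Ad4-primed participants: 3/18 = 16.7% (95% CI 3.6 to 41.4), against 3/24 = 12.5% (2.7 to 32.4).
- If p1 and p0 are the same in both arms, the arm rates are identical and their difference is 0, whatever Ad4 does.
- Zero events, upper limit 1 − 0.025^(1/n): n = 36 gives 9.7%; n = 12 gives 26.5%.

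Per-time-point counts do not give the endpoint either. A participant with a Grade 3 reaction after two vaccinations appears in two rows, so the rows cannot be summed to a number of participants.

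**The case against.** The best case on the other side has four parts.

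- **The SAR wording is a local slip.** Section 13.3.3 itself points to Table 5, 13.3 speaks of non-serious ARs, and 12.6 lists severe ARs separately from SARs. All of these presuppose related events that are not SARs. This makes the literal reading unlikely to be intended. It does not remove the contradiction, and a trial-wide hold depends on the label.
- **Worst-case coding is conservative.** It cannot hide harm, and it acts only when the same event recurs with discordant grade and causality. That is correct. It is still a one-directional error in a primary endpoint, and easily avoided.
- **The SAP does not forbid by-group results.** Its arm-split sentence follows the additional tabulations of all adverse events, some of which combine time points, and it reports related SAEs over the whole study period. Protocol 14.5.4 still applies. What stands is that the SAP specifies neither by-group safety results nor intervals. SAP 3.2 also allows groups A and D to be expanded for more safety data; both are in Arm 1, so an arm split could not separate them.
- **The 36 v 12 summary is in neither document.** It pools one to three Ad4 doses, and Protocol 14.3 disclaims confidence about group differences. It should therefore be descriptive only.

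**Conclusion.** All three points stand, as corrections to rules and not as evidence of error in any result.

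1. Protocol 13.3.3 contradicts 13.3.1 and Tables 4 and 5, and the conflict reaches the hold rule in 12.6.
2. Protocol 14.5.4 can only inflate the Grade 3-4 endpoint. The size of the inflation is unknown because the documents give no rates of recurrence or discordance.
3. SAP 12.2.2 falls short of Protocol 14.5.4 on intervals and grouping, and its time-point counts do not match an endpoint defined over the study.

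A reader might go further in four ways that the documents do not support.

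- *That both primary endpoints are miscounted because of the SAR label.* The Grade 3-4 endpoint uses grade and relatedness, not the label. The other counts vaccine-related SAEs, with seriousness judged separately; nothing says it is derived from the label, and the SAP does not use the term SAR.
- *That a hold is close to certain.* Any such probability needs an assumed event rate, and the literal reading of 13.3.3 to prevail over the sections that contradict it.
- *That 14.5.4 also triggers holds.* It is a rule for analysis and reporting.
- *That the SAP's safety tables pool the controls.* Tables 2.1 and 2.2 are titles only. The pooling is in the text of 12.2.2.

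**What to change.** - **Protocol 13.3.3, 13.3.1, Tables 4 and 5, and 12.6:** reconcile them so that one definition of SAR applies throughout, then check how 12.6 reads under it. What should trigger a hold is for the sponsor and investigators to decide. If dosing is complete, check any event recorded as an SAR against the Table 4 criteria.
- **Protocol 14.5.4, and state it in the SAP:** derive Grade 3-4 and related for each occurrence before collapsing repeats. Count a participant only if a single occurrence meets both conditions.
- **SAP 12.2.2:** report each primary safety endpoint once per participant over the whole study, overall and by group A-H, with two-sided Clopper-Pearson 95% intervals (including for zero counts). Keep the time-point tables as supporting detail. Add a descriptive summary of Ad4-primed (36) v placebo-primed (12) participants in Part 1.
- **SAP Tables 2.1 and 2.2:** add shells that show this layout.

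The cost is a wording correction to the protocol, a few sentences in the SAP and two table shells. No new data are needed, since severity and causality are already assessed for each event.

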**TABLE 4 TYPES OF ADVERSE EVENTS AND DEFINITIONS**

Type of Event	Definition
Adverse Event (AE)	
Any untoward medical occurrence in a patient or clinical trial subject to whom a medicinal product has been administered including occurrences that are not necessarily caused by or related to that product.
 
The Principal Investigator will use the following criteria when deciding whether to report a laboratory parameter that falls outside the normal range according to the local laboratory guidelines as an adverse event:
 
 
- If it is clinically significant and Grade 1 (or above) according to the grading system in Appendix 1 the abnormal result will be recorded as an AE
 
-
 

Adverse Reaction (AR)	
Any untoward and unintended response to an investigational medicinal product related to any dose administered.
 
'Related' means possibly, probably or definitely as defined below.
 
All solicited adverse events which start within 7 days of a vaccination will be automatically classified as an adverse reaction.

1 An abnormal result will be deemed to be clinically significant if any of the following apply:

- The test result is associated with relevant accompanying symptoms
- Additional diagnostic tests or medication are indicated

- As a consequence of the test result, an immunisation is delayed or further immunisations are discontinued
- The investigator considers the result to constitute an adverse event for any other reason

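### Protocol section 13.3.3 labels every related non-solicited event an SAR whatever its seriousness, against Tables 4 and 5, and the label feeds the trial-wide hold in section 12.6

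*Protocol*

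**What the plan says.** Protocol section 13.3.3 opens with its scope: "The investigator must assess the causality of all non-solicited adverse events or reactions in relation to each of the trial IMPs". For the meaning of each category it points to Table 5. It then gives two branches. The first reads "If the causality assessment is unrelated or unlikely to be related, the event is classified as an AE". The second reads "If the causality is assessed as possible, probable or definitely related, then the event is classified as an SAR".

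Table 5 has a row for each causality category. The row whose description reads "There is evidence to suggest a causal relationship and the influence of other factors is unlikely" (Probable) and the row reading "There is clear evidence to suggest a causal relationship and other possible contributing factors can be ruled out" (Definitely) both carry the type AR, as does the Possible row.

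Table 4 defines an adverse reaction as "Any untoward and unintended response to an investigational medicinal product related to any dose administered", and counts the same three categories as related. It defines an SAR as an adverse reaction that also meets one of the listed seriousness criteria. Solicited events that start within 7 days of a vaccination are ARs automatically.

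Section 13.3 has non-serious ARs recorded in the source documents and CRF, and SAEs and SARs notified within 24 hours. Section 13.3.1 has the investigator assess seriousness first, against Table 4.

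Section 12.6 uses the label: "All trial immunisations will be put on hold in the event of a SAR or two severe ARs", and again for each later SAR or severe AR.

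**The concern.** The same event receives two different labels depending on which part of section 13 is applied. A mild, non-serious, non-solicited event judged possibly related is an AR under Tables 4 and 5 and an SAR under the last sentence of 13.3.3.

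The label has consequences. Under section 12.6 a single SAR holds every immunisation in the trial, whereas ARs do so only if they are severe, and at first only when there are two. A hold then brings expert review, notice of a temporary halt to the regulator, and a substantial amendment before dosing can resume. SARs also carry 24-hour notification. If the sentence is followed as written, a mild event sets all of this in motion. If some staff follow the sentence and others the tables, whether the trial halts depends on which page was read.

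**Working it through.** The documents state no figure that depends on this rule, so there is none to reproduce. The check is a comparison of passages, followed by an illustration of scale.

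**Step 1: one event followed through each passage.** Take a mild, non-serious, non-solicited event judged possibly related.

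| Place in the protocol | Result |
|---|---|
| 13.3.3, last sentence | SAR |
| Table 5, Possible row | AR |
| Table 4 | AR; not an SAR, because no seriousness criterion is met |
| 13.3 | Non-serious AR, recorded in source documents and CRF |
| 13.3.1 | Seriousness is decided first, against Table 4; the event is not serious |

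**Step 2: can 13.3.3 be read as covering serious events only?** No. Its scope is all non-solicited events, and its unrelated branch gives AE, not SAE. A paragraph written for serious events would have given SAE there.

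**Step 3: what the label changes.**

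| Consequence | If labelled SAR (13.3.3) | If labelled AR (Tables 4 and 5) |
|---|---|---|
| Hold under 12.6, mild or moderate event | Yes, on the first event | No |
| Hold under 12.6, one severe but non-serious event, none before | Yes | No; two severe ARs are needed |
| 24-hour SAR notification (13.3) | Yes | No, unless the event is on the separate list of important events in 13.2 |

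**Step 4: which events are exposed.** Only non-solicited ones. Solicited events with onset within 7 days are made ARs by Table 4 and do not pass through the 13.3.3 rule.

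**Step 5: illustration of scale.** Input from the protocol: n = 48 in Part 1 (60 with the 12 in Part 2). Assumption, not in the documents: each participant independently has probability p of at least one related, non-serious, non-solicited event. The chance that at least one participant has such an event is 1 − (1 − p)^n.

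| Assumed p | n = 48 | n = 60 |
|---|---|---|
| 1% | 1 − 0.99^48 = 38% | 45% |
| 2% | 1 − 0.98^48 = 62% | 70% |
| 5% | 1 − 0.95^48 = 91% | 95% |
| 10% | 1 − 0.90^48 = 99% | 99.8% |

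These are chances that a triggering event occurs. They become chances of a hold only if staff apply 13.3.3 literally.

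**Step 6: the safety endpoint.** Section 14.2.1, and SAP sections 10.1.2 and 12.2.2, word the endpoint as vaccine-related SAEs. An SAE must meet a Table 4 criterion. The endpoint therefore does not refer to the 13.3.3 label at all.

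**The case against.** The strongest reply is that this is one stray letter. Table 4, Table 5, 13.3 and 13.3.1 all separate relatedness from seriousness, and 13.3.3 itself directs the investigator to Table 5. Section 12.6 distinguishes an SAR from severe ARs, and that distinction would do no work for non-solicited events if every related one were already an SAR. Trained staff working from the tables would trigger none of the consequences. Most expected mild reactions are solicited ones, which lie outside the rule when they start within 7 days.

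Much of this stands. A drafting slip is the likeliest explanation, and the probabilities above rest on assumed rates and a literal reading. What does not follow is that nothing needs doing. The sentence is a current instruction, it cannot be confined to serious events, and it bears on a rule that halts the trial.

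A reader might go further and infer that 13.3.3 redefines the primary endpoint and fills the count of vaccine-related serious events with mild ones. The documents do not support that. The endpoint is worded as SAE plus relatedness and carries its own seriousness requirement. It would be inflated only if events labelled SAR under 13.3.3 were counted as SAEs in the analysis. The SAP does not spell out how the class is derived, which is a reason to confirm it but not evidence that it goes wrong.

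A reader might also infer that a hold is close to certain. That depends on the assumed rate: at 1% the chance of even one such event in Part 1 is 38%.

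**Conclusion.** The contradiction is real. For related non-solicited events, 13.3.3 gives a label that Tables 4 and 5, 13.3 and 13.3.1 do not give. It is an inconsistency of wording, probably unintended, and not a deliberate design choice. The consequence at stake is the section 12.6 hold, together with 24-hour SAR notification: read literally, one mild event would trigger both.

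The size cannot be fixed from the documents. The range of 38% to 99% for at least one such event among 48 participants rests on assumed rates of 1% to 10%, on independence between participants and, as a chance of a hold, on literal application of the sentence. The vaccine-related SAE endpoint stands as worded.

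**What to change.** Reconcile the last sentence of 13.3.3 with Tables 4 and 5 and section 13.3.1, so that causality and seriousness are separate steps wherever they appear and the class that feeds the 12.6 hold is unambiguous. Section 12.6 already names its triggers; this point asks for no new hold rule and takes no position on what the rule should be.

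In the SAP or its programming specification, confirm that the vaccine-related SAE endpoint is derived from the Table 4 seriousness criteria plus relatedness, and not from the label assigned under 13.3.3.

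The cost is a one-sentence protocol correction, a note to site staff, and one line on the endpoint derivation. SAP section 3 describes conduct at the site in the past tense. If dosing is complete, the confirmation of the endpoint derivation is the part that still affects the results.
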